### **3.2.7 Adverse Event Reporting to the IRB**

Any adverse event that is assessed as MACCE or AAME will be reported by the investigator or sponsor to the IRB of the study center, along with a description and an analysis of the adverse event. The IRB will review the reported adverse event, evaluate it, and make recommendations for further clinical trial follow-up or withdrawal of the subject from the study.

## **3.3 Early Withdrawal of a Study Participant**

A study participant may withdraw from the study at any time during the study and for any reason, whether identifiable or not, by their own free will. This decision and the patient's independent choice are presented in the informed consent form.

A study participant may also be withdrawn early from the study if there is persistent non-adherence to the study follow-up and treatment procedures (see Chapter 2.5.6, Withdrawal from the Study Due to Non-Adherence to Treatment).

A study participant may be withdrawn early from the study based on a clearly stated justification by the investigator or the study sponsor if it is in the patient's best interests to discontinue the study.

The basic reasons for withdrawal from the study are considered as follows:

- If any abnormal study result, symptom, or measurement parameter is detected and resolution, improvement, correction or stabilization of which may require a long period of treatment and/or observation and will change the course of the study-defined follow-up and treatment;
- Any adverse event that may persist during the follow-up period, or require a change or discontinuation of the study-defined treatment, or disrupt the study-defined clinical evaluation plan, or be associated with a severe outcome.
- Any adverse event that may be masked by the use of different medical care regimens than those specified in the study protocol;
- If study treatment intervention, it may pose an expected AAME, a health threat, requiring discontinuation and modification. These conditions require modified treatment measures and regimens other than those specified in the study, including hospitalization. In addition, clinical conditions that may be characteristic of AAME may be exclusion criteria from the study.
- An adverse event related to treatment with P2Y12 inhibitors is a study endpoint, after which the study-planned follow-up is no longer required.
- The MACCE determines the study endpoint, and further measures are no longer required.

In these cases, study participants are discontinued from the study-planned follow-up; the necessary assessments of early withdrawal from the study should be conducted, and the reason for early withdrawal from the study should be determined (evaluated). In these cases, the patient continues to be monitored and treated by the medical support team.

The investigator will describe and analyze the reason for the study participant's early withdrawal, which is part of the routine medical records. An adverse clinical event will be registered in the study data form.

The investigator will inform the study participant of the decision to withdraw from the study early and about further follow-up and treatment measures.

Patient data collected before withdrawal will be used for study purposes, with confidentiality, following the procedures provided and the terms presented to the patient in the informed consent form.

### **3.4 Definition of Study Completion**

The expected end of the study for a participant is determined by the date at the end of the 12-month follow-up period. However, in cases of early withdrawal, this period may be shorter.

Generally, the end of the study is determined by the end of the 12-month follow-up period for the last subject in the study.

## **4.0 Study Monitoring and Evaluation**

The study is monitored and evaluated by a team established by the study sponsor.

Monitoring and evaluation activities include communication with the principal investigator and study personnel, follow-up of study processes, data collection and registration at selected clinical centers (sites), control of the accuracy and quality of data collection, assessment, and reporting of adverse events that occurred during the study to the study sponsor.

Centralized and on-site monitoring procedures at study sites will be aimed at:

- Assessing the risks of data collection and collection -

- Assessing the data collection process using routine medical records, data registration forms, electronic databases, and communication tools;
- Identifying deviations and inconsistencies from the protocol of the current study procedures -
  - Observing the operational processes of the study sites and processing and analyzing the accompanying information;
- Reviewing the adequacy, quality, and effectiveness of research data sources -
  - Assessing the adequacy and effectiveness of the use of study center resources (including personnel) for research data collection;
- Monitoring the implementation of legal communication, rights, and security measures with research participants -
  - Monitoring and evaluating the medical care and documentation of subjects related to the research.

Monitoring and evaluation activities carried out in these areas will

- Avoid or reduce potential risks to data quality and integrity and research processes.
- Identify additional measures to ensure the safety of research procedures and data quality for research participants.
- Avoid data collection anomalies (e.g., non-random or inappropriate data sources) and risks of patient rights or safety violations;

Various monitoring methods will be used to eliminate the risks of errors in the study: the collection, integrity and processing of critically important data. To this end, during the implementation of the study, the sponsor

- identifies critical data and research processes for monitoring;
- develops a monitoring and evaluation plan;
- assesses possible risks;
- implements monitoring procedures;
- evaluates the monitoring results and again identifies critical processes and conditions for adjustment/improvement.

Critical data and processes for monitoring and evaluation in all cycles will be considered:

- Procedures for obtaining informed consent from the subject to participate in the study;
- Screening measures, application of inclusion and exclusion criteria;
- Processes for random allocation of research subjects and disclosure of research results;
- Compliance and reporting of the use of the investigational product;
- Documentation and reporting of study endpoints;
- Assessment and reporting of abnormal study results and adverse effects/events (serious or non-serious) within the study;
- Collection and documentation of medical care and study results outside the study;
- Assessment and reporting of procedures for early withdrawal from the study;
- Protection of confidentiality and security of study data;

Planned monitoring activities at study sites will be carried out at 4-6 week intervals. Its procedures will enable the collection of data on study processes, the detection of errors in the processing of study data, the detection of inconsistencies between primary data sources and study data forms, the review of study documentation, the observation of procedures, and the assessment of compliance with the study protocol.

The monitoring processes at the study sites will be based on the following procedures:

- Communication with investigators and research personnel -
  - To review and monitor research activities at various stages of initiation and progress of the study. Centralized monitoring can enhance and support communication through teleconferencing, videoconferencing, and email.
  - Communication with research personnel does not discuss the clinical context, diagnosis, or treatment approaches of an individual patient (research subject);
- Review of the appropriateness of processes, procedures, and data records at the research site -
  - From screening, randomization, use of the study product, and determination of study endpoints;
  - Review the appropriateness of informed consent forms for participation in the study.
  - Evaluation and validation/rejection of primary sources of research data;
  - Reporting of medical care and examination results outside the scope of the study in primary sources of research data;
  - Response to abnormal results and adverse events (serious or non-serious) of the study as part of the study safety assessment measures and procedures (Chapter 2.5.8 Safety Assessment and Control) will assess all cases of risk:
    - Abnormal results of the study, MACCEs and AAMEs;
    - Medical care or diagnostic tests performed outside the scope of the study;
    - Non-adherence to medical treatment;
    - Early withdrawal of the subject from the study;
    - Violation of independent choice, confidentiality and illegal processing of study data;

## 5.0 Informed Consent

Study participant informed consent is obtained by the Declaration of Helsinki, the International Conference on Harmonisation of Clinical Research (ICH) Good Clinical Practice (ICH GCP for Clinical Research), the laws of Georgia [27-30] and this study protocol.

The study sponsor prepares the informed consent form. After approval by the Medical Ethics Council (the Biomedical Research Ethics Committee of Tbilisi State Medical University), it is submitted to the IRB of the study centers. Its written form and verbal consent constitute a formal document for obtaining the study participant's informed consent.

The study centers will maintain the informed consent forms and relevant protocols approved by the National Medical Ethics Council, along with other documents.

To obtain consent, study participants (or their legal representatives) will be provided with narrative, explanatory information and a written informed consent form, and explanations about the study will be provided upon request before participating in the study.

Properly completed, written informed consent will be obtained from study subjects before they participate in the study activities.

According to Georgian legislation [28,31], the legal representative of the research subject is considered to be family members (spouse, children, parents, grandparents - from the circle of first-degree heirs), relatives (sister, brother - in cases where there are no first-degree heirs) or a person who is legally supported by the person, a guardian or a person entrusted with trust, who will be known by the assignment agreement - power of attorney or trustee.

## 6.0 Informing the IRB

The study protocol, the participant consent form and, upon request, all documents regulating the study activities and procedures approved by the Medical Ethics Board will be submitted to the study center's IRB.

All documents issued by the IRB will be kept throughout the study period, along with other study documents. Through them, the investigator will receive confident evidence of compliance with existing regulations of the study procedures.

Throughout the study period, any MACCE, UAME, and all observable or voluntary adverse clinical events will be reviewed by the study center's IRB. It will review these events and, if necessary, present a position on ethical issues of study case management.

Before the start of the study, the investigator must have a written study protocol and informed consent form approved by the IRB, which will then be used to initiate the activities envisaged by the study.

If changes to the protocol and informed consent form are necessary, they will not be used in the research process until the IRB has reviewed the changes, if necessary, with the participation of the study sponsor, eliminated provisions containing risks to the study participant, and approved the changes to the documents in written form.

In addition to making changes, updates or additions to the research protocol and informed consent form, the IRB should, as necessary, review, indicate to the study sponsor, and amend other previously received documents that may be affected by the changes to the research protocol and informed consent form.

The IRB may request revisions to the protocol or other research documentation if content received from various information channels will be related to risks for study conducting activities or present conditions

that may affect study participant's safety. In addition, the IRB may require an annual review of research documents for the purpose of updating them or completing the study.

## 7.0 Study Records and Reports

### 7.1 Record Keeping and Data Processing

The data record form (DRF) will be filled in with the data from the study results of each study participant, the form and structure of which will be the same for all subjects and study centers.

At the study center, the data provided in the DRF will be collected and recorded by the study center investigator, who is directly involved in the study participant screening, randomization and follow-up. The study center investigator confirms the completeness, accuracy and authenticity of the entered study data by signature and date.

The principal investigator reviews, signs and dates each completed form. His signature will confirm the responsibility of the study sponsor for the completeness and relevance of the study data (clinical, laboratory, other) entered in the DRF.

The fields allocated for data recording in the DRF are structured according to the name, periods of study activities and the entry date. It provides spaces for recording clarifications, comments or conclusions. Data is entered into the form from primary sources of clinical information and medical documentation used in real-world practice.

In case of omission, non-use or inaccuracy of study data in the DRF, a record confirming their existence is checked in the primary source of data (medical record, authenticated result of the conducted examination, other source of registration of the study result, e.g., result registration journals, electronic databases). In such cases:

- If there are records in the primary data sources, they are transferred to the clinical data report form and the data are marked as "filling in the omission".
- If there are no corresponding records in the primary data sources, within a reasonable time frame (+2 weeks), it can be conducted through the corresponding examination and recording of the results in the DRF by the envisaged plan. In such a case, the data is marked as "filling in the unused".
- If there are no relevant records in the primary data sources and it is not possible to conduct the relevant examination and obtain the data within a reasonable time frame (+2 weeks) according to the research plan, "omission" is indicated in such a case.
- If data is entered in the DRF, but there is no such data in the primary source and it is possible to conduct the relevant examination and record the results as data within a reasonable time frame (+2 weeks) according to the study plan, the recorded result is considered true data, transferred to the DRF as "modified, true". The previous data will be cancelled, which will be confirmed by the investigator's signature and date.
- If data is entered in the clinical case registration form, but there is no such data in the primary source, and it is not possible to conduct the corresponding examination and record the results in the form of data within a reasonable time frame (+2 weeks) according to the study plan, the data entered in the registration form will be marked as "false".

False data will not be processed, used neither for the study, nor for reporting, nor for the discussions planned for the study. During the monitoring and evaluation period, the number of missing and false data will be calculated for each CRF and will be reported if the number of such data exceeds 10% of the unique data planned for the study.

The primary source of data is considered to be the study participant's medical record, which must be produced in accordance with applicable regulations and must chronologically reflect the results of clinical examinations and interventions conducted both within and outside the scope of the study, clinical findings and observation results, laboratory/instrumental diagnostic examination results (including diagnostic examinations included in this study), results of specialized consultations, clinical judgments, medical prescriptions (including treatment included in this study), treatment results, and results of medical care provided outside the research center (in other institutions) throughout the entire period of the study.

Within the study, the patient's medical record is considered the primary documentary source of study data. Its constituent documents will include original medical records, including, but not limited to: hospital care records, medical care charts and forms produced by a doctor's or clinic's office, doctor's notes, diaries, checklists, drug prescription forms and prescriptions, treatment regimens and regimens, printouts of automated diagnostic instruments, laboratory and instrumental examination reports and forms reflecting the results. All records in the DRF must be searchable, readable and consistent with the medical record.

The study data will be collected, stored and processed in a special electronic database. It will include a data entry platform with a similar design to the DRF, however, data entry validation will be carried out not by the name of the data, but by its encrypted code. Once in the database, the name of each data variable will be reflected only in encrypted code without a readable name or textual explanation, so that the data cannot be identified.

The electronic database file will be located away from the research centers. Authorized investigators and study monitoring and evaluation team members will have access to enter and process data through electronic signature authorization.

Data will be entered into the electronic database under the DRF design. Data will be placed with a unique study participant number and without patient identification data, it will not be possible to read the identifiers.

The electronic database will not be connected to the Internet or any other network. The aggregation and import of data collected in the study centers will be carried out from working files. Such an interim file will only collect data from individual subjects enrolled in a single study center, and for the current period. In these files, the subject will be identified only by their unique study number. After data aggregation in the electronic database, the working file will be destroyed.

The identifiers of the study participant, marked with a unique code, and the names and descriptions of the data variables marked with unique codes will be placed in separate files and remotely from the main study database. They will be fully protected. Only authorized investigators will be allowed to access them.

The study database will be processed only for the purposes of the study and for the performance of procedures specified in the protocol.

After the completion of the study data collection, the electronic files containing the personal identification data of the study participants will be deleted. Subsequently, this data will be stored in a secure space only in hard copy for 1 year after the end of the study.

After the study is completed, the DRFs, filled in with the relevant data and confirmed by signatures, will be collected by the sponsor from the study centers and stored centrally for 2 years.

The electronic database of the study data, without the identifiers of the study subjects, will be stored for further processing for scientific purposes for an indefinite period after the study is completed.

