#### **2.4.3 Inclusion Criteria**

Inclusion criteria define the clinical model according to which the study subject will be selected. The criteria will equalize cardiovascular risk disease/condition and co-morbidities that may distinguish and exclude CAD severity.

A patient will be selected for the study participation if they meet all of the following inclusion criteria:

- Participants of both sexes aged between 35-80 years are eligible for the study.

[and]

- Diagnosed with chronic coronary artery disease;

[and]

- Completed informed consent form for participation in the study;

[and]

- Undergone elective PCI within the last 12 weeks without procedure-related complications; or the clinical challenge is to de-escalate post-PCI antiplatelet treatment from an alternative P2Y12 inhibitor to clopidogrel.

[and]

- LVEF $\geq$ 38% after index PCI;

Atherosclerotic coronary artery lesion confirmed by coronary angiography and coronary artery stenting performed within 12 weeks without clinically significant procedural complications are determined by the results of relevant PCI. De-escalation of antiplatelet treatment from an alternative P2Y12 inhibitor to clopidogrel can be easily detected by the prescription order from routine clinical practice.

Complementary, this inclusion criterion also represents clinical evidence of CAD medication treatment.

The selected participant should be characterized by echocardiographically confirmed normal or clinically mild left ventricular systolic dysfunction or preserved systolic function after the index PCI. Assessment of systolic function should be assessed by the standard echocardiographic measurements of left ventricular ejection fraction. Echocardiography should be performed as part of the screening measures of the potential study participant before randomization.

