- Number of study participants who experienced major bleeding (Major Bleeding) within a 12-month of the study follow-up;

- Number of study participants who experienced non-major bleeding (Non-major Bleeding) within a 12-month of the study follow-up;
- Number of study participants who experienced a heart failure event (Heart Failure Event) within a 12-month of the study follow-up;
- Number of study participants who experienced percutaneous coronary intervention or coronary artery bypass-grafting (Repeated Coronary Revascularization) within a 12-month of the study follow-up;

Pre-specified endpoints of the study are defined as:

- Number of study cases in each arm with a composite of death from any cause, myocardial infarction, stroke, or major bleeding (Net adverse clinical events - NACEs) within a 12-month of the study follow-up;
- Number of study cases in each study arm with a composite of death from any cause, myocardial infarction, or stroke (Major adverse cardiac or cerebral events - MACCEs) within a 12-month of the study follow-up;
- Number of study participants who reported their health status as good or satisfactory, or with the appearance of CVD symptoms, or with a significant inability to self-care (Patient-Reported Health Status) at 3, 6 and 12 months of the study follow-up;
- Number of study participants self-reported angina not required hospitalization (Patient-Reported Angina Not Required Hospitalization) at 3, 6 and 12 months of the study follow-up;
- Number of study participants reported last week's shortness of breath due to heart failure not requiring hospitalization (Patient-Reported Heart failure Severity) at 3, 6 and 12 months of the study follow-up;
- Number of study participants withdrawn from the study for any reason within a 12-month of the study follow-up;
- Costs of clinical service utilization for case management during the study follow-up;
- Costs incurred for incremental services, including costs for the major adverse cardiovascular and cerebrovascular event;

Along with studying the effectiveness of CYP2C19 genotype-guided treatment selection with clopidogrel and an alternative P2Y12 inhibitor, clinical case management processes in the real-life healthcare system and factors that positively and negatively impact the processes will be evaluated: healthcare processes, place of care, delivery of medical procedures, medication use, and management of comorbidities.

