### **3.2.4 Abnormal Test Results**

An individual abnormal result of a study alone cannot be considered an adverse event. An abnormal result of the study is classified as an adverse event if it meets one or more of the following criteria:

- accompanied by relevant clinical symptoms;
- requires specific diagnostic evaluations, or therapeutic measures, such as surgical intervention, or additional drug or non-drug treatment, which is not recommended and considered for the treatment of the disease/condition of study interest and provided in the framework of study procedures;
- an effect changes or terminates the treatment intended for the study or the conditions of participation of the study subject (for example, when an abnormal study result determines the study exclusion criteria);
- considered as an adverse event by the sponsor or investigator of the study;

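### For missing or unsourced values, section 7.1 lets an examination up to 2 weeks later stand as the value of the earlier time point, with no exception for screening or time-dependent variables

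*Combined protocol and SAP*

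**What the plan says.** Section 7.1 (Record Keeping and Data Processing) distinguishes five situations:

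- The source holds the value: it is transferred to the form.
- Neither form nor source holds it, but the test can still be done: "within a reasonable time frame (+2 weeks), it can be conducted through the corresponding examination", and the result is labelled 'filling in the unused'.
- Neither holds it and the test cannot be done in time: it is marked as an omission.
- The form holds a value without source support ("If data is entered in the DRF, but there is no such data in the primary source") and a repeat is possible within +2 weeks: "the recorded result is considered true data, transferred to the DRF as" 'modified, true'. Then "The previous data will be cancelled", with signature and date.
- As the fourth, but no repeat is possible: the entry is marked 'false' and not used.

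The same section has missing and false items counted for each form and reported if they exceed 10% of the planned data.

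Elsewhere, the Synopsis (Follow-up) sets visits at 3, 6 and 12 months, each ±1 week. Section 2.3.2 establishes eligibility before randomisation. Section 2.4.3 adds: "Echocardiography should be performed as part of the screening measures of the potential study participant before randomization". Under section 2.5.4, results are disclosed to participants and the care team after randomisation and genotyping.

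**The concern.** A measurement taken later is not the value at the visit. It may be useful data, but it belongs to its own date. The second and fourth situations in section 7.1 attach it to the earlier time point, and the fourth also removes the entry it replaces.

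This matters most at baseline. A screening test that was missed or left without a source could be done after allocation, on the assigned drug and with the arm known, and still be filed as screening data. The form is completed by the site investigator who is directly involved in screening, randomisation and follow-up.

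It matters next for quantities that change over days or weeks, such as blood count and creatinine. The adherence questionnaire (section 2.5.6) asks about medication taken in the past week, and one patient-reported endpoint counts participants who "reported last week's shortness of breath due to heart failure". If these are repeated later, the answers describe a different week.

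**Working it through.** The plan gives no figure to reproduce. The check is a comparison of passages plus one piece of date arithmetic.

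**1. Which values are affected.** Of the five situations, only the second and fourth put a later result in an earlier slot. Both require that the primary source holds no record. A value with a laboratory report, instrument printout or clinic note is transferred and kept.

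**2. Late result against visit window.** The allowance is +2 weeks (section 7.1) and the window ends at nominal date +1 week (Synopsis). Section 7.1 does not say which date the 2 weeks run from.

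- From the nominal date: latest result at +2 weeks; 2 − 1 = 1 week outside the window.
- From a visit held at the late edge: 1 + 2 = +3 weeks; 3 − 1 = 2 weeks outside.
- From a visit held at the early edge: −1 + 2 = +1 week; 1 − 1 = 0, still inside.
- From the day the gap is found: the documents set no upper limit.

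**3. Screening values.** Appendix 2 schedules blood count, HbA1c, creatinine/eGFR, ECG, echocardiography and the adherence questionnaire at screening. Apart from a medical examination, none of these recurs at the randomisation visit. Section 7.1 applies to form data in general and sets no cut-off at randomisation. The interval from screening to randomisation is not stated. A replacement therefore falls after randomisation whenever randomisation comes before the repeat test. Sections 2.3.2 and 2.4.3 show that this is not intended, but section 7.1 contains nothing that stops it.

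**4. Oversight.** The 10% trigger counts missing and false items. A gap filled by a late test is no longer missing, and a replaced entry is labelled true rather than false. Neither adds to the count, so any number of substitutions can occur without a report.

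**5. Consistency of the rule.** The same unsourced entry is 'false' and unused if no repeat is possible, but gives way to a different measurement called true if one is. Whether a repeat is feasible two weeks later says nothing about the patient's state at the visit.

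**The case against.** The strongest reply is that this is a data-repair rule with safeguards. Sourced values are kept. Substituted values carry distinct labels, and cancellation is signed and dated. The repeat must follow the study plan, and other sections put eligibility before randomisation. All of this stands, and it limits the point to missing or unsourced values and to a gap left open rather than an instruction. It does not close the gap: the study-plan wording names no cut-off, and a label does not restore the correct date.

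It is also fair to say that a visit window and a repair allowance govern different things. Calling them a contradiction would be too strong; the point is that a repaired value can count for a visit although it lies outside that visit's window.

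Several stronger readings are tempting, and the documents do not support them:

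- That transient safety changes are overwritten. A fall in platelets or haemoglobin with a laboratory report is a sourced value and stays. Section 3.2.3 also requires all abnormal results to be recorded and followed. Only an undocumented value can be replaced.
- That the rule opens a route to exclusion after allocation through section 3.2.4, whose example reads "for example, when an abnormal study result determines the study exclusion criteria". That section defines when an abnormal result is classed as an adverse event; it does not authorise exclusion. Withdrawal for abnormal findings already exists independently, in sections 2.4.4 (diabetes control at follow-up) and 3.3.
- That the problem can be sized from the site-visit interval ("Planned monitoring activities at study sites will be carried out at 4-6 week intervals") or from the 10% trigger. Section 2.6.3 has data evaluated continuously as they are entered, so discovery need not wait for a site visit. The trigger does not count these substitutions at all.

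**Conclusion.** The point holds in this limited form: for values without a source record, section 7.1 can turn a late measurement, taken with allocation known, into baseline or visit data. The displacement is up to 1 week beyond the visit window if the allowance runs from the nominal date, and up to 2 weeks if it runs from a visit at the late edge.

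The number of values affected cannot be estimated, because the documents give no expected rate of missing or unsourced entries. The co-primary endpoints are deaths and the secondary endpoints are clinical events; a repeat examination cannot replace either. What is exposed is baseline and eligibility data, follow-up laboratory, ECG and echocardiographic values, and the past-week questionnaires. Including the questionnaires assumes that 'examination' in section 7.1 covers them, which the text does not settle. A single shifted adherence answer is unlikely to decide a withdrawal, since section 2.5.6 considers withdrawal only for repeated non-adherence and after review.

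The rule should be changed, because it is a stated rule that mislabels the timing of data. It does not threaten the primary result.

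**What to change.** Replace the second and fourth situations in section 7.1 with the following:

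- A late result is entered under its actual examination date as an unscheduled assessment. It counts for a visit only if it lies within that visit's ±1 week window.
- No screening or baseline value may be filled in or replaced after randomisation.
- An unsourced entry stays readable and is flagged 'source not found'. It is left out of the main analysis, and a sensitivity analysis includes it.
- Substituted values are counted in the 10% data-quality trigger.

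The cost is one paragraph of wording and a flag, which can build on the labels, dates and comment space already in the form, plus a few more missing visit values. Sample size, endpoints and scheduled procedures do not change.
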